## Study Questionnaires

Participants will complete the following questionnaires in REDCap:

- State-Trait Anxiety Inventory (STAI): This is a 40-item scale that measures both state and trait anxiety.
- Pain Anxiety Symptoms Scale (short form PASS-20): This is a 20-item scale that assesses fear in association with pain.
- Multidimensional Assessment of Interoceptive Awareness, Version 2 (MAIA-2) [26]: This is a 37-item multidimensional instrument that includes 8 scales ranging from 3 to 7 items each. The scales are noticing, not-distracting, not-worrying, attention regulation, emotional awareness, self-regulation, body listening, and trusting.
- Body Awareness Questionnaire (BAQ): This 18-item scale measures attention to bodily processes
- The Autism Quotient (AQ): The AQ has been observed to negatively correlate with baseline OT concentrations.
- Adapted version of Longing for Interpersonal Touch Questionnaire: This questionnaire assesses touch received and desired in the last week. This questionnaire has been modified to remove gendered language.

# Heat pain calibration

Ratings of heat stimuli will be collected to determine a moderately painful heat stimulus for use in pre- and post-sensory testing. Ascending and descending series of 10s heat stimuli (32-50°C) will be presented on the arm until pain intensity is rated '70' on the visual analog scale (VAS) pain intensity scale.

## Baseline measures will occur at the ACTRI and will take approximately 30 minutes to complete.

## Sessions 1 and 2/ Sensory testing with oxytocin or saline

Participants will be greeted and seated in a comfortable reclining position.

*Urine pregnancy test:* Due to the risks of OT on a pregnancy, participants with the potential to become pregnant will undergo a urine pregnancy test at the beginning of both sessions. Participants with a positive pregnancy test will be dismissed.

**Baseline assays for peripheral oxytocin**, *inflammation, and metabolic features:* Blood (approx. 10mL) will be collected from all participants at the beginning of Sessions 1 and 2 to conduct ELISA immunoassay to measure baseline OT concentrations, as well as baseline IL-6 (a pro-inflammatory cytokine) and metabolic features (approx. 20mL blood drawn total in study).

**Baseline heart monitoring**: Participants will then undergo a 5-min baseline monitoring period during which resting heart rate will be monitored, using a Bionomadix wireless ECG system from Biopac (or equivalent). Heart rate will be continuously recorded in a time-locked manner throughout the session and used to calculate heart rate variability during affective touch and pain in either session.

## VAS measures:

Participants will be asked to make the following ratings throughout the session:

Intensity of the touch sensation: "No sensation" (far left) to "Most intense sensation imaginable" (far right)

Unpleasantness of the touch sensation: "Extremely unpleasant" (far left) to "Neutral" (middle) to "Extremely pleasant" (far right)

Pain intensity: "No pain" (far left) to "Most intense pain imaginable" (far right)

Pain unpleasantness: "Extremely unpleasant" (far left) to "Neutral" (middle) to "Extremely pleasant" (far right)

*Skin monitoring*: Photos will be taken of the participant's arm before and after injection to document the possibility of any adverse response. Photos will not show any other part of the body other than the arm and will be deleted from the smartphone the same day as the session and stored on secure computers by subject ID, like our other PII. In the case of an adverse reaction, the study physicians will grade the severity of reaction as advised by the FDA.

# Pre-sensory testing

*Anxiety ratings* will be collected using VAS rating scales for fear of pain (1 = "no fear of pain" to 100 = "extreme fear of pain") and state anxiety (1 = "extremely calm" to 100 = "extremely anxious")

# Affective touch perception:

Affective touch testing will be comprised of 2 trials of 15s slow brushing and 2 trials of 15s fast brushing on each dorsal forearm, in a random order. After each trial participants will rate the (un)pleasantness and intensity of the sensation on VAS scales.

## Pain perception:

*Mechanical pain threshold (MPT):* MPT will be determined using weighted pinprick stimuli exerting forces of 8, 16, 32, 64, 128, 256 and 512 mN. Stimuli will be applied for 2s on and 2s off until the first percept of sharpness (pain) is reported.

*Temporal summation:* Temporal summation will be tested using a standard 256mN pinprick stimulus applied for 10 repetitions of 1s each, over the same 1cm^2 area. The participant will provide pain ratings for a single

pinprick and for the 10 repetitions, using the VAS rating scales described above. This procedure will be repeated 3 times and the mean pain rating used.

*Pressure pain threshold (PPT):* PPT will be tested using a pressure algometer placed over the dorsal forearm muscles (e.g. extensor digitorum), and pressure will be increased until pain is reported.

*Heat pain threshold (HPT)*: HPT will be tested using a high-quality QST thermode. To establish HPT, the thermode will be placed on the arm at a baseline of skin temperature (automatically calibrated by the thermode) and will be increased until the stimulus is reported as painful by the participant. The mean of three trials will be taken as the HPT.

*Heat pain ratings:* Three 10s trials of the individually calibrated pain-70 heat stimulus will be rated using the VAS rating scales for pain intensity and (un)pleasantness described above.

*Injection of Oxytocin or saline control:* Either 4mcg/2ml OT *OR* 2ml isotonic saline (0.9% sodium chloride; placebo control) will be injected into the middle of the dorsal forearm. Sessions will be separated by at least 48 hours to ensure drug clearance. Both participants and experimenters will be fully blinded with respect to OT versus saline placebo session/order. OT and saline will be prepared by the Investigational Drug Service at the ACTRI. OT will be prepared by diluting commercially available synthetic oxytocin (OXYTOCIN- oxytocin injection, solution from Fresenius Kabi USA, LLC or equivalent manufacturer supplied by the ACTRI research pharmacy; see uploaded package insert). The injection will be performed by a licensed healthcare provider. Saline placebo will be drawn from SODIUM CHLORIDE- sodium chloride injection, solution from B. Braun Medical Inc or equivalent manufacturer supplied by IDS pharmacy (see uploaded package insert).

Blood pressure and oxygenation will be monitored before and after OT injection and at approximately 5 minute intervals (BP) or continuously (pulse ox) for the remainder of the session.

**Post-sensory testing:** Perception of pain and gentle brushing will be tested beginning ~10min after injection on the injected arm, given timing of OT effects in prior studies, and then on the control arm. A post-block baseline sensory test will be conducted, identical to the affective sensory testing described above. All testing will be conducted within a ~3-4cm^2 sized region of skin proximate to the injection site on the dorsal forearm. At the end of testing, the injected arm will be observed by a licensed provider to confirm normal sensation and lack of any adverse response to OT injection.

# Sessions 1 (after baseline) and 2 will occur at the ACTRI and will take approximately 1 hour each to complete.

## Participant Randomization:

The schedule of randomization will be created and accessed by an ACTRI pharmacist only. Males and females will be randomized without replacement across a block of 20 codes (assuming 20% attrition) using an Excel-based random number generator. All subjects will receive OT in one session and saline placebo in the other in this within-subject cross-over study. Subjects will be randomized to one of two session orders (Session 1 OT and Session 2 saline; Session 1 saline and Session 2 OT). Randomization will be stratified so that each sex will have their respective list of randomization codes. Session order (blinded code) will be tracked in the Screening/Enrollment Log maintained by the study coordinator(s) and identity of the orders will be revealed by the pharmacy at the conclusion of the study.

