## Timeline

To ensure drug clearance, Sessions 1 and 2 (OT; saline placebo or saline placebo; OT) will be separated by more than two days according to the participant and experimenters' availability. After providing written consent (active enrollment), subjects will have 4 months to complete Sessions 1-2. Sessions will be offered to healthy volunteers until our sample size of 20 healthy volunteers has been reached. These sessions will be filled on a first-come-first-served basis.

1-2 years will be required for recruitment, data collection, and analysis.

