# Sample Size Determination & Power

We expect that pleasantness ratings of C-LTMR-optimal touch will be significantly increased after local OT injection and that pain perception will be reduced. In published studies, differences in postsurgical pain after local infiltration with OT versus control resulted in very large mean differences in VAS pain ratings of Cohen's d = 3 to 4.5. In spinal nerve ligation (SNL) model rats, interplantar injection of OT versus control resulted in mean differences in paw withdrawal threshold of Cohen's  $d = 13.8^{19}$ . In addition, intranasal oxytocin (24IU) increases pleasantness of touch stimuli (especially driven by negative stimuli), with an estimated Cohen's d of  $\sim 3^{23}$ . Although these are very large effect sizes, accounting for sampling variability and differences in proposed study design (acute pain; healthy adults; subcutaneous OT administration), we powered the study to detect a large effect size of d = 0.8. Assuming a within-subject correlation of 0.5 and an attrition rate of 25%,

the proposed sample size of N = 20 will provide 0.8 power to detect an effect size as small as d = 0.8 based on a two-sided  $\alpha = 0.05$ .

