
## **10. HUMAN SUBJECTS**

## **Subject Population**

A total of 20 healthy adults, ages 18-65, will complete two separate test sessions in a within-subject crossover study. Equal numbers of males and females will be recruited. Data will be analyzed to determine if sex is a significant predictor of study outcomes. We will include all genders, races, and ethnicities.

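### The randomization text does not secure balanced session order within sex, because the meaning of the 20-code block and the allocation ratio are left open

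*Combined protocol and SAP*

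**What the plan says.** All references are to the combined protocol and SAP.

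- Section 9, Participant Randomization, describes the list in one sentence: "Males and females will be randomized without replacement across a block of 20 codes (assuming 20% attrition) using an Excel-based random number generator". It adds that "Subjects will be randomized to one of two session orders" (OT then saline, or saline then OT) and that "Randomization will be stratified so that each sex will have their respective list of randomization codes". It gives no allocation ratio and no smaller block, and does not say whether 20 is the length of each list or of both together. The pharmacist alone creates and accesses the schedule.
- Section 10, Subject Population: "A total of 20 healthy adults, ages 18-65, will complete two separate test sessions in a within-subject crossover study", and "Equal numbers of males and females will be recruited". That means about 10 per sex.
- Section 9, Timeline: "Sessions will be offered to healthy volunteers until our sample size of 20 healthy volunteers has been reached".
- Section 9, Sample Size Determination & Power, uses 25% attrition where the randomization text uses 20%, and states that "the proposed sample size of N = 20 will provide 0.8 power to detect an effect size as small as d = 0.8".
- Section 9, Data Analyses and Interpretation, names time (pre/post) as the predictor and age and race/ethnicity as potential covariates in all analyses. It names no session, period or order term.

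**The concern.** A block guarantees balance only when it is used up. With about 10 people per sex, a 20-code list for each sex would be left half used, and the split between the two orders among the codes drawn would be left partly to chance. A single 20-code block shared by both sexes would balance overall but not within sex, which defeats the stratification. The pharmacist who builds the list cannot tell from the text which arrangement is meant.

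Order matters because the two sessions are not alike. Session 1 follows consent, questionnaires and heat calibration, and it is the first exposure to the study injection and the full test battery. If the response to injection or to repeat testing differs between first and second session, balanced order keeps that difference out of the OT-versus-saline comparison. Since no session term is planned, it is the main stated protection. Subject Population also plans to examine sex as a predictor, and unequal orders within sex would mix sex with order.

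**Working it through.** **Inputs.** 20 codes, two orders, separate lists by sex (Participant Randomization); 20 people, equal by sex (Subject Population, Timeline); d = 0.8, correlation 0.5, two-sided 0.05, 25% attrition (Sample Size). Assumption not in the documents: each list is split evenly between the two orders.

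**The plan's own figure first.** The standardized paired difference is 0.8/√(2(1 − 0.5)) = 0.8. A paired t-test needs n = 15 for power of at least 0.80 (power 0.821), and 15/0.75 = 20. The stated N = 20 reproduces, with attrition already inside it.

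**Reading A: 20 codes per sex, 10:10, first 10 used.** The number of OT-first codes among the 10 drawn is hypergeometric, P(k) = C(10,k)·C(10,10−k)/C(20,10).
- P(5:5) = 252²/184,756 = 0.344.
- P(6:4 either way) = 2 × 210²/184,756 = 0.477.
- P(7:3 or worse) = 1 − 0.344 − 0.477 = 0.179. For at least one sex: 1 − (1 − 0.179)² = 0.326.
- Using 12 codes per sex, to replace dropouts, changes little: exact balance 0.350, 8:4 or worse 0.170.

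Convolving the two sexes gives the overall split of 20. Simple randomization is shown for comparison.

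| Overall split | Reading A | Simple randomization |
|---|---|---|
| 12:8 or worse | 0.350 | 0.503 |
| 13:7 or worse | 0.118 | 0.263 |
| 14:6 or worse | 0.028 | 0.115 |

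**Reading B: 20 codes in total, 10 per sex, split 5:5.** If every code is used, order is exactly 5:5 per sex and 10:10 overall.

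**Reading C: one shared block of 20, 10:10.** Overall 10:10 when used up. Within a sex of 10 the same hypergeometric applies, so 5:5 has probability 0.344.

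**Effect on power at n = 20.** For a session-adjusted crossover estimate with n1 and n2 per order, the noncentrality is 0.8/√((1/n1 + 1/n2)/4) on n1 + n2 − 2 degrees of freedom, and relative efficiency is 4·n1·n2/N².
- 10:10: power 0.922.
- 12:8: efficiency 4 × 96/400 = 0.96, power 0.912.
- 13:7: efficiency 4 × 91/400 = 0.91, power 0.897.
- Averaged over Reading A: power 0.915.

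**Effect on bias without a session term.** Let τ be the OT effect and π the Session 2 minus Session 1 difference in the pre-to-post change. OT-first people have expected OT-minus-saline τ − π; saline-first people have τ + π. With n1 OT-first, the mean is τ − π(n1 − n2)/N. The share of π carried is 4/20 = 20% at 12:8 and 6/20 = 30% at 13:7.

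**Dropout.** Even from 10:10, if 5 of 20 leave at random, the completers split 9:6 or worse with probability 2 × (0.1354 + 0.0163) = 0.303. At 9:6 the share is 3/15 = 20%.

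**Small blocks, 10 used per sex.** Blocks of 2 give exactly 5:5. Blocks of 4 give 5:5 with probability 2/3 and never worse than 6:4 within a sex. Overall they give 10:10 with probability 0.50, 11:9 with 0.444 and 12:8 with 0.056.

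**The case against.** The strongest reply is that the list sentence names one block for males and females together, so 20 codes may mean 10 per sex, matching the 20 volunteers. If each list is split 5:5 and fully used, there is no imbalance among those randomized. This stands as a possible reading. It is not stated, and neither is the even split it needs. The separate-lists sentence and the attrition remark leave a 20-code list per sex equally open.

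A reader might go further and infer that no reading works, because 20 completers at 20% attrition need 20/0.8 = 25 codes. The documents do not support that. The power statement already builds attrition into N = 20, and 20 codes less 20% leaves 16, above the 15 completers it needs. Subject Population does say that 20 will complete, but that is an inconsistency between enrolled and completing numbers, not proof that the list fails.

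It is also fair to say that a half-used long block is better than chance (13:7 or worse in 12% against 26%), and that the average power loss is under one point (0.922 to 0.915).

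Finally, each session has its own pre-injection tests, and post-injection testing covers a control arm. In Session 1, consent, questionnaires and calibration all precede the pre-test, so a stable shift in ratings cancels in the pre-to-post change. That stands too. What does not cancel is a session effect on the change itself; where the control arm is used as the reference, that effect must also differ by arm. The documents give no estimate of its size.

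**Conclusion.** The point holds in limited form. As written, the randomization text does not secure balanced session order within sex at the planned size. On the per-sex reading exact balance occurs in 34% per sex, 7:3 or worse in 18% per sex, and 12:8 or worse overall in 35%. On the shared reading the within-sex figure is the same 34%. Only ten codes per sex, split 5:5 and fully used, avoids the problem. These figures assume an even split in each list and about 10 codes used per sex.

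Two stronger readings should be resisted. The text does not establish that each sex has a 20-code block, and a clearly unequal split is possible rather than likely (13:7 or worse, 12%). Nor is this a power problem: power stays near 0.90 or above up to 13:7 with 20 people. What remains is an ambiguous instruction to the pharmacist and a conditional bias: 20% to 30% of any session effect on the pre-to-post change at 12:8 to 13:7, in an OT-minus-saline contrast with no session term. The stated N = 20 is unaffected. This is a nearly free improvement to the plan, not a fatal flaw.

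**What to change.** 1. In Participant Randomization, replace the 20-code block with a separate 1:1 list for each sex in small permuted blocks, for example sizes 2 and 4 randomly mixed and known only to the pharmacist. This keeps order near balance under any stopping point.
2. State the length of each list. If 20 completers are intended, each sex needs 10/0.8 = 12.5, so 13 codes at 20% attrition, or 10/0.75 = 13.3, so 14 at 25%. Blocks of even size round 13 up to 14.
3. Use one attrition figure throughout, and say whether 20 means enrolled or completing.
4. In Data Analyses and Interpretation, include session (period) in any OT-versus-saline comparison. Small blocks do not protect against unbalanced dropout; this term does. Session order is already to be logged for each participant.

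The cost is a few minutes of pharmacist time, a few protocol sentences and one model term. With 20 people at 10:10, adding that term moves power from 0.924 (paired t) to 0.922. Predictability from small blocks is a minor worry: only the pharmacist sees the schedule, the trial is double-blind, and everyone receives both treatments.

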## Blinding:

This is a double-blinded study. The ACTRI nurses, research technicians, participants and investigators will be blinded to the study material until after the statistical analysis is performed. Subjects will be blinded to study material by being injected by the nurses. Oxytocin and saline are both clear fluids and will be administered in Identical syringes. The study coordinator will submit a prescription to the pharmacy for the correct session day.

Pharmacists will deliver the study drug in a blinded fashion, and the doctor or nurse will subsequently administer the study drug to the subject keeping the doctor/nurse, subject, coordinator, and research assistants blinded until trial completion.

## Timeline

To ensure drug clearance, Sessions 1 and 2 (OT; saline placebo or saline placebo; OT) will be separated by more than two days according to the participant and experimenters' availability. After providing written consent (active enrollment), subjects will have 4 months to complete Sessions 1-2. Sessions will be offered to healthy volunteers until our sample size of 20 healthy volunteers has been reached. These sessions will be filled on a first-come-first-served basis.

1-2 years will be required for recruitment, data collection, and analysis.

## **Endpoints:**

Primary Endpoint: When all data for the primary and secondary outcomes are collected and statistical analyses of these data are complete.

#### Outcome Measure(s)

#### Primary Outcomes:

- Pleasantness ratings of slow (primary) and fast gentle brushing
- Pain perception assessed in response to noxious pinprick (primary), pressure, and heat stimulation.
- Pain intensity and (un)pleasantness will be assessed with visual analog scales (VAS) as follows: pain intensity [anchors "no pain" (far left) to "most intense pain imaginable" (far right)] and (un)pleasantness ["extremely unpleasant" (far left) to "neutral" (middle) to "extremely pleasant" (far right)]. 100-point VAS scales are common, validated, and reliable measures of pain.

#### Key Secondary Outcomes:

All questionnaires will be administered using the Research Electronic Data Capture (REDCap) platform facilitated by study personnel, before or during Session 1. They include the following:

- State-Trait Anxiety Inventory (STAI; a measure of both state and trait anxiety)
- Pain Anxiety Symptoms Scale short form (PASS-20; an assessment of fear of pain)
- Multidimensional Assessment of Interoceptive Awareness (MAIA-2; a measure of interoceptive sensibility)
- The Body Awareness Questionnaire (BAQ; a measure of attention to bodily processes)
- Autism Quotient (AQ; observed to negatively correlate with baseline OT concentrations).
- .

# Sample Size Determination & Power

We expect that pleasantness ratings of C-LTMR-optimal touch will be significantly increased after local OT injection and that pain perception will be reduced. In published studies, differences in postsurgical pain after local infiltration with OT versus control resulted in very large mean differences in VAS pain ratings of Cohen's d = 3 to 4.5. In spinal nerve ligation (SNL) model rats, interplantar injection of OT versus control resulted in mean differences in paw withdrawal threshold of Cohen's  $d = 13.8^{19}$ . In addition, intranasal oxytocin (24IU) increases pleasantness of touch stimuli (especially driven by negative stimuli), with an estimated Cohen's d of  $\sim 3^{23}$ . Although these are very large effect sizes, accounting for sampling variability and differences in proposed study design (acute pain; healthy adults; subcutaneous OT administration), we powered the study to detect a large effect size of d = 0.8. Assuming a within-subject correlation of 0.5 and an attrition rate of 25%,

the proposed sample size of N = 20 will provide 0.8 power to detect an effect size as small as d = 0.8 based on a two-sided  $\alpha = 0.05$ .

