## **Data Analyses and Interpretation**

General Statistical Approaches. Data will be analyzed descriptively and analytically. Descriptive statistics (means and standard deviations for continuous and proportions/counts for categorical outcomes) will be used to describe outcomes at baseline. Weighted generalized estimating equations (WGEE) will be employed, with appropriate link functions depending on the type of the response (e.g., identity for continuous and logit for binary outcome), to examine longitudinal changes in an outcome and longitudinal association between outcomes in regression analysis, controlling for covariates for Aims 1-2. Unlike parametric models such as generalized linear mixed-effects models (GLMM), the semi-parametric WGEE requires no distribution assumption and yields valid inference for a broader class of data distribution under the missing at random mechanism^123. WGEE provides valid inferences under the missing at random (MAR) mechanism^124. We will use WGEE to test the missing completely at random (MCAR) assumption and will use the generalized estimating equations (GEE), if the MCAR is not rejected. GEE involves fewer parameters and provides more efficient inference than WGEE. Given the small sample size for Aims 1-2, we will complement the usual asymptotic inference with clustered bootstrap to improve inference validity and report the bootstrap inference if it differs from its asymptotic counterpart. We set  $\alpha$ =0.05 for all analyses and use Holm-Bonferroni adjustments for <= 5 tests and False Discovery Rate (FDR) for > 5 tests. When correlated outcomes are analyzed (e.g., outcomes in related domains), corrections will be calculated based on the effective number of independent tests that account for correlations between the outcomes. Whenever possible, effect size will be reported in addition to point and interval estimates. All analyses will be performed using the latest versions of R^129 and SAS. Hypothesis Testing. For Aim 1, separately for OT and saline placebo sessions, we will compare changes in ratings of pain over time between the OT and control arm using WGEE, where time (one binary indicator) will be the predictor, controlling for covariates. A significant time effect, tested using appropriate linear contrasts, will support the hypothesis that the OT injection has effects on the outcome. We will follow with *post hoc* analyses to estimate the effect size of the OT injection. For Aim 2, we will apply the same approach in Aim 1 to pleasant touch outcome. Age and race/ethnicity will be included as potential covariates in all analyses.

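### The analysis tests change within each session and names no oxytocin-versus-saline contrast; the 0.8 power is correct for one paired contrast but is tied to no planned test

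*Combined protocol and SAP*

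**What the plan says.** Aims 1 and 2 (Section 6) each compare subcutaneous OT with saline placebo. Under Participant Randomization (Section 9), every subject receives both, in randomised session order.

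Data Analyses and Interpretation sets out the Aim 1 analysis "separately for OT and saline placebo sessions". Within that, "we will compare changes in ratings of pain over time between the OT and control arm" by weighted GEE, "where time (one binary indicator) will be the predictor, controlling for covariates". The decision rule is: "A significant time effect, tested using appropriate linear contrasts, will support the hypothesis that the OT injection has effects on the outcome". Aim 2 uses the same approach. For multiplicity the plan will "use Holm-Bonferroni adjustments for <= 5 tests" and "False Discovery Rate (FDR) for > 5 tests", with a further correction for correlated outcomes. It does not define the family of tests. Outcome Measure(s) marks two outcomes as primary: pleasantness of slow brushing and pain from pinprick.

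Sample Size Determination & Power starts from this: "Assuming a within-subject correlation of 0.5 and an attrition rate of 25" per cent. At a two-sided alpha of 0.05 it concludes that "the proposed sample size of N = 20 will provide 0.8 power to detect an effect size as small as d = 0.8". It does not name the outcome, the contrast, the scale of d or any multiplicity adjustment.

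On numbers, Participant Randomization assumes 20% attrition, Subject Population (Section 10) has 20 adults completing both sessions, and Timeline does not say whether its 20 are enrolled or completing.

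**The concern.** A model fitted within the OT session, with time as its only named predictor, estimates how ratings moved from before to after the injection. That movement mixes any OT effect with the effect of a needle and 2 ml of fluid, of repeated noxious testing, and of expectation. The saline session exists to separate these, but the plan never compares the two sessions formally. As written, the rule could therefore declare an OT effect that saline would have produced equally.

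The second difficulty is that a reader cannot say which test has 0.8 power. The analysis text describes two different contrasts (a time effect and a comparison of changes between arms) and a multiplicity rule that the power statement does not use. A null result could then be read as evidence against d = 0.8 when the test actually run was not powered for it.

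**Working it through.** Power is from the noncentral t distribution, two-sided. The paired t-test stands in for weighted GEE; covariates and the bootstrap were not modelled.

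**1. The plan's own figure.** Inputs from the power section: d = 0.8, correlation 0.5, attrition 25%, N = 20, alpha 0.05.
- dz = d/√(2(1 − ρ)) = 0.8/√(2 × 0.5) = 0.8.
- Completers: 20 × 0.75 = 15.
- Power at n = 15 is 0.821; at n = 14 it is 0.790. So 15 is the smallest n reaching 0.8, and 15/0.75 = 20. The figure reproduces.

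**2. What each contrast isolates.**

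| Contrast | In the plan? | What remains mixed with OT |
|---|---|---|
| Post minus pre, OT session | Yes, as the time effect | Injection, repeat testing, expectation |
| Difference in changes, injected versus control arm, OT session | Described, but not expressed by a single time indicator | Needle and fluid volume, present only in the injected arm |
| OT versus saline session | Not named | Neither, given randomised order (period effects can be modelled) |

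The plan's linear contrasts cannot supply the third row: a model fitted to one session has no between-session parameter.

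**3. Size of the attribution problem.** Assume a non-specific pre-post change of dz = 0.5 and no OT effect.
- At n = 15 the OT-session time effect is significant at 0.05 with probability 0.438.
- If saline shows the same change and the two results are independent (assumed), OT is significant and saline is not with probability 0.438 × (1 − 0.438) = 0.246.

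**4. Power of the comparison of changes, if d is on the single-rating scale.** With unit variances, variance = 4(1 − r_prepost − r_sametime + r_crosstime) and dz = 0.8/SD. At n = 15, alpha 0.05:
- All correlations 0.5: SD = √2 = 1.414, dz = 0.566, power 0.53. Detectable d = 1.414 × 0.778 = 1.10.
- All 0.6, 0.7, 0.8: power 0.63, 0.75, 0.90.
- Pre-post 0.5, same-time 0.5, cross-time 0.25: SD = 1, power 0.82.
- If d is already on the change-score scale, dz = 0.8 and power is 0.82.

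**5. Alpha.** With one family per aim, alpha stays 0.05 and paired power stays 0.82. If the two primary outcomes form one family (assumed), the first Holm step is 0.05/2 = 0.025, where power is 0.72.

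**6. Completers.** For the single paired contrast: 15 (25% attrition) gives 0.82; 20 × 0.80 = 16 gives 0.85; 20 gives 0.92.

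**7. A test that fits the aims.** Regress the OT-minus-saline difference in post-injection values on the same difference in pre-injection values, and test the intercept. With same-time between-session correlation r_b, within-session pre-post correlation r_w and cross-session cross-time correlation r_c, residual variance = 2(1 − r_b) − [2(r_w − r_c)]²/[2(1 − r_b)]. All correlations are assumed; n = 15, d = 0.8, simulated power:

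| r_b = r_c | r_w | Residual variance | Power at 0.05 | Power at 0.025 |
|---|---|---|---|---|
| 0.5 | 0.5 | 1 − 0 = 1.00 | 0.79 | 0.67 |
| 0.5 | 0.8 | 1 − 0.36 = 0.64 | 0.93 | 0.87 |
| 0.3 | 0.5 | 1.4 − 0.16/1.4 = 1.29 | 0.68 | 0.56 |
| 0.3 | 0.8 | 1.4 − 1/1.4 = 0.69 | 0.91 | 0.84 |

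A period term lowers each by about 0.01.

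**The case against.** The plan runs the same model in the saline session, so a non-specific effect could show itself there. The wording about changes between the OT and control arm also points to a within-person control. Both points have force, but neither closes the gap. Significance in one session and not in the other is not a test of their difference (step 3). The arm comparison removes what both forearms share, but not the effect of the injection itself, and the stated decision rule rests on time.

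A reader might infer that the true power is 0.53, or that the smallest detectable d is 1.10. The documents do not support that. Those values need the comparison of changes to be the test, d to be on the single-rating scale and all four ratings to correlate at 0.5. The plan states none of these for a four-rating contrast, and other admissible choices give 0.82 or more. For pain, even four ratings are an inference: pre-injection brushing is specified on each forearm, but the pre-injection pain tests are not said to be done on both.

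A reader might likewise infer that Holm cuts power to 0.72. That needs both primary outcomes in one family, whereas each maps naturally to its own aim, and the correction for correlated outcomes could soften any adjustment. Nor does the attrition conflict undermine the sample size, since every reading gives at least 0.82 for the single contrast.

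Finally, the background calls this a pilot project. It nonetheless states hypotheses, an alpha, multiplicity control and a power claim, so the primary contrast should be named.

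**Conclusion.** The concern holds as a problem of specification. No named test answers the OT-versus-saline question in either aim, and the stated rule could credit OT with a non-specific change. The 0.44 and 0.25 probabilities illustrate this under an assumed dz of 0.5, and the second also assumes independent sessions. They are not predictions.

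The 0.8 power is correct on its own inputs. What is missing is its link to a planned test, a scale for d and a test family. The 0.53 to 0.90 range for the comparison of changes (n = 15, alpha 0.05, d on the single-rating scale, common correlation 0.5 to 0.8) measures that ambiguity and does not show an error. The attrition discrepancy is minor. The plan should be corrected before unblinding.

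**What to change.** (a) In Data Analyses and Interpretation, make the primary test for each aim the between-session contrast, OT versus saline, on the injected arm's post-injection outcome, adjusted for the same session's pre-injection value and with a period term. Keep the injected-versus-control-arm comparison as supporting evidence, because both aims concern local effects. State which pinprick measure is primary (threshold or rating), and confirm that the injected forearm receives the pre-injection pain tests.

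(b) In Sample Size Determination & Power, restate power or detectable d for that test, giving the scale of d, a range of correlations, the test family and the alpha after adjustment. As an illustration with 15 completers and the correlations assumed in step 7, power is about 0.68 to 0.93 at 0.05, slightly less with a period term. With between-session and cross-time correlations of 0.5 and no period term, detectable d is about 0.81 down to 0.65 at 0.05, and 0.92 down to 0.73 at 0.025, as the within-session correlation rises from 0.5 to 0.8.

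(c) Use one attrition figure in Participant Randomization and in the power section. Say whether the 20 codes are in total or per sex, and whether 20 is enrolled or completing in Timeline and Subject Population.

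The cost is wording and a possibly less favourable stated power. No participants are added, and no measurements provided that the injected forearm is already tested before injection.
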